The present discussion will primarily focus on evaluation of the hypotheses using the main outcome measures (a) subjective craving (single-item 100 mm visual analog scale), (b) heart rate, (c) systolic and diastolic blood pressure, and (d) skin conductance. Since these measures were collected twice during the CCE, a mean and peak value was computed for each (in recognition of the possibility that medication effects could impact either the average or the maximum response, or both). These summary values were then used to compute difference scores for the mean and peak response by subtracting the mean/peak of the retrieval CE session from the mean/peak value obtained in the test CE session or the follow-up CE session.

Therefore, negative difference scores would indicate a response decrement from the retrieval to the test or follow-up session whereas positive scores would indicate a response increment. Panel A and B of figure 1 depicts the mean (solid symbols) and peak (empty symbols) craving and heart rate difference scores, respectively, for propranolol (squares) vs. placebo (circles) treated groups. The figure shows and independent samples t-tests confirmed (all p values in figure) that (i) the propranolol treated group evidenced a greater decrement in mean and peak craving than did the placebo treated group, and (ii)

the mean and peak heart rate increase evidenced by the propranolol treated group was significantly smaller than in the placebo treated group. Panels A and B of figure 2 depict the systolic (SBP) and diastolic blood pressure

Figure 1

[figure not shown]
[figure not shown]

Figure 2

(DBP) mean and peak difference scores, respectively, by group. Analyses confirmed that the mean SBP and DBP decreased significantly in the propranolol treated participants relative to the placebo treated individuals. Analyses also verified a trend towards a similar decrease in the peak responses on these measures. No group differences were detected for mean and peak SC (all p 's > .4).

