Video & In Vivo Stimuli: The combination of video and in vivo cocaine cues used in the R21 will also be used in the proposed study (see figure 4). These cues will be presented in all CCE sessions (unlike the picture-based novel CCE, described below, which occurs only in test/follow-up CCE sessions). The video cocaine cues will consist of a 5-min. video depicting cocaine use in a variety of settings. The in vivo cocaine cues will consist of a small bag of simulated crack cocaine, the participant's preferred style of crack pipe, a lighter, and money (\$20 bill) for those who use crack cocaine. For powder or IV users, simulated powder cocaine, cocaine paraphernalia, and money will be used. During the in vivo cue presentation, the cocaine cues will be placed on the table directly in front of the participant and they will be asked to inspect and handle (with non-dominant hand) the cues for a five-minute period.

Picture Stimuli: A picture-based novel CCE will be administered at the end of all test/follow-up CCE session (described below) to determine if any observed DoR effects generalize to cocaine cues not previously experienced by the participants. The picture cues depict individuals of varied race and gender using crack or powder cocaine. The pictures will be categorized by route of administration and presented to participants according to their individual route of administration. A total of 12 novel pictures will be presented (10 seconds each) on a video screen located directly in front of the participant (the picture order will be counterbalanced across participants). Thus, the duration of the novel picture-based CCE will be 2 min. Heart rate and SC will be continuously measured for the first 50 sec of the picture presentation, as this is where the largest response is likely to occur. At the conclusion of the picture viewing participants will be prompted to complete the same assessments they completed following the video/in vivo CCE sequences (See Figure 4).

[figure not shown]
The pictures used in this exposure sequence will be derived from a library of 48 pictures (12 pictures will be presented in each test/follow-up CCE session; thus, participants will not see any picture more than once) that we have either developed or acquired from publically available sources.

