Our research group has previously used this type of picture-based cue exposure procedure to successfully elicit craving in methamphetamine dependent individuals.^{69,70} Additionally, previous research by our group has shown that these pictures (subset of 10) elicit greater cocaine craving and subjective arousal in cocaine dependent individuals ($n = 27$; craving $\bar{x} = 5.9$ and arousal $\bar{x} = 10.1$) than in non-cocaine dependent controls ($n = 28$; craving $\bar{x} = .06$ and arousal $\bar{x} = 5.3$; both t 's > 3.6 , both p 's $< .001$). Furthermore, the mean craving and arousal reported by cocaine dependent individuals in response to the cocaine pictures was greater than the mean craving and arousal they reported in response to a set of neutral comparison pictures (craving $\bar{x} = 1.0$ and arousal $\bar{x} = 5.3$; both t 's > 4.5 , both p 's $< .0001$). Thus, we are confident these cocaine picture cues will serve as effective elicitors of craving and arousal in proposed study.

Procedure: At approximately 10:00 am, baseline subjective and physiologic outcome measures will be collected. Thirty minutes later, participants will receive the first sequence of CCE. Each sequence will consist of a 5-min video cocaine cue presentation followed immediately by in vivo cue presentation. Heart rate and SC data will be continuously collected during the first 50 sec of each cue type (video and in vivo). The CDMS Scale and BP will be obtained at the end of the in vivo cues. After the latter measures were obtained participants remained comfortably seated until the second, identical sequence of CCE commenced (approximately 5-10 min later). At the end of the CCE in the retrieval session, participants will receive their medication and complete all outcome measures. As indicated in figure 4, all dependent measures will be obtained immediately after CCE sequence and at 15 min. and 30 min. time points following termination of CCE. At the end of each retrieval session, research staff assisted the participant in removing the HR/SC leads and BP cuff. Participants will remain at the CTRC laboratory facility for an additional 60 min., at which time a blood draw will occur. The sample will

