Heart rate (HR), blood pressure (BP) and skin conductance (SC) were measured as indices of physiological arousal during each CCE session. Heart rate was collected via two electrodes, with one affixed to the right shoulder and the other on the bottom left side of the participant's ribcage. Blood pressure was measured using an intermittently inflatable cuff. Because this measure cannot be obtained unobtrusively, it will be taken at the same time as the CDMS is obtained (see figure 4 above). Skin conductance was recorded using Ag/AgCl electrodes attached to the skin over the metacarpal bone of the fifth digit, non-dominant hand. Since physiological arousal/reactivity was likely to be greatest in the earliest portions of a CCE sequence, HR and SC data will be continuously collected during the initial 50-second epoch of each video and in-vivo cue presentation and during the first 50-sec of the novel picture-based CCE (they also are collected at baseline and at 15-min and 30-min follow-up time points; see figure 4). The HR and SC signals will be amplified using the ECG 100c and GSR 100c Modules of the Biopac MP100 data acquisition system; the Biopac system will be interfaced with an Apple (MacBook Pro) laptop for data storage and subsequent reduction. While the HR, BP and SC measures obtained in the second medicated retrieval session may be impacted by the medication (not in the first retrieval session since the medication is administered after the CCE), it should be noted that these responses are not relevant to the evaluation of any hypothesis. Nonetheless, these responses will likely provide some measure/indication of the effects of the first medicated retrieval.

G. Participant Compensation

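### The in vivo cues are handled with the hand that carries the skin-conductance electrodes, and no artefact rule is stated

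*Combined protocol and SAP*

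**What the plan says.** Section 3.D (Video & In Vivo Stimuli) puts simulated cocaine, paraphernalia and money on the table in front of the participant; "they will be asked to inspect and handle (with non-dominant hand) the cues for a five-minute period".

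Section 3.F (Physiological Measures) gives the only electrode placement in the document: "Skin conductance was recorded using Ag/AgCl electrodes attached to the skin over the metacarpal bone of the fifth digit, non-dominant hand". The same paragraph sets the recording window: "HR and SC data will be continuously collected during the initial 50-second epoch of each video and in-vivo cue presentation". The Procedure text in 3.D gives the same 50-second window for both cue types. It also makes each session two video-plus-in-vivo sequences: after the first, "participants remained comfortably seated until the second, identical sequence of CCE commenced".

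In test/follow-up sessions a picture exposure is added, in which nothing is handled: "Heart rate and SC will be continuously measured for the first 50 sec of the picture presentation". SC is also taken at baseline and at 15 and 30 minutes after the cues.

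Section 3.H (Outcome Measures) lists SC with heart rate and blood pressure as a physiological outcome, to be summarised by mean and peak. First-retrieval-session summaries serve as baseline covariates. It mentions a data-reduction step for heart rate and SC without describing it. The Data Analysis Plan for hypothesis 1 names heart rate and systolic and diastolic pressure, not SC.

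**The concern.** SC is measured at the skin surface, so moving or loading the electrode hand can register as signal. Under the plan as written, the hand that picks up the bag, pipe, lighter or banknote is the hand being recorded, and recording covers the opening of the handling period. Nothing in the text delays handling, asks that the electrode hand be kept still, or says how movement artefact is detected and removed.

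What is at stake is the precision and readability of the familiar-cue SC outcome. Artefact could enter both the outcome and the first-session covariate used to adjust it. It could raise a peak summary directly if the peak is taken from an affected epoch. Familiar-cue and novel-picture SC would also differ in movement as well as in cue type, which complicates comparison of the two. The plan shows concern for stable recording elsewhere: 3.D has participants sit quietly for about 20 minutes before baseline.

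**Working it through.** The plan gives no figure to reproduce. The check is a comparison of sections and a count of epochs.

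**Sections side by side**

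| Item | Where | What is stated |
|---|---|---|
| Hand that handles the cues | 3.D, Video & In Vivo Stimuli | non-dominant |
| Hand with SC electrodes | 3.F, Physiological Measures | non-dominant, over the fifth metacarpal |
| SC window | 3.D Procedure and 3.F | first 50 s of each video and each in vivo presentation |
| Delay before handling | – | none stated |
| Artefact rule | 3.H, Outcome Measures | unspecified data reduction only |

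The first three rows together make the handling hand the recorded hand in every in vivo SC epoch.

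**Share of cue-period epochs affected**

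- Familiar cues, any session: 2 sequences × (1 video + 1 in vivo) = 4 epochs, of which 2 are in vivo. 2/4 = 50%, or 100 s of 200 s.
- Test/follow-up session with the picture epoch: 4 + 1 = 5 epochs. 2/5 = 40%.
- Whole study: 2 retrieval sessions and 4 test/follow-up sessions (the first test, then weeks 1, 3 and 6). Total epochs = 2 × 4 + 4 × 5 = 28. In vivo epochs = 6 × 2 = 12. 12/28 = 43%.

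**What the noise could be (illustration only)**

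Assume independent epochs with ordinary noise variance e, equal cue signal in both cue types, and extra variance ke in each in vivo epoch. Assume also that the SC mean pools all four familiar-cue epochs. The documents give no k and do not spell out the pooling.

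- Four-epoch mean: [2e + 2(e + ke)]/16 = e(4 + 2k)/16.
- Two video epochs only: 2e/4 = 8e/16.
- Ratio of the first to the second: (4 + 2k)/8.

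| k | Four-epoch mean | Video only | Ratio |
|---|---|---|---|
| 0 | 4e/16 | 8e/16 | 0.50 |
| 1 | 6e/16 | 8e/16 | 0.75 |
| 2 | 8e/16 | 8e/16 | 1.00 |
| 5 | 14e/16 | 8e/16 | 1.75 |
| 10 | 24e/16 | 8e/16 | 3.00 |

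The table covers epoch-level noise only. It leaves out variation between participants, so it does not convert into lost power for a group contrast. Its use here is to show that dropping the in vivo epochs helps only when k exceeds 2 and costs precision below that.

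**The case against.** The strongest reply is that little depends on this. SC is not in hypothesis 1's named list, the sample size rests on craving (3.B), and every arm follows the same procedure. That stands, and it limits the point to one outcome's precision. A reader might infer a bias in favour of one arm or a threat to the main hypothesis test; the documents support neither.

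Several SC recordings involve no handling: the video epochs, the picture epoch, baseline, and the 15- and 30-minute points. So it would be too strong to say that any SC null is unreadable, or that half of all cue-period SC is affected. Half is exact only for the familiar cues, and the novel-picture SC analysis is not touched.

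A reader might also take the R21 result (section 1.C: "No group differences were detected for mean and peak SC") as evidence that movement masked an effect. The documents report that null without linking it to movement, and it does not show a masked effect.

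Some links in the argument are inferred. Movement within the recorded 50 seconds follows from the ordinary meaning of handling objects, but no grip or timing is described. Pooling of video and in vivo epochs is the natural reading of 3.H, not a stated rule. The undescribed data reduction might include artefact screening. A handling effect that is stable within a participant would be partly removed by the first-session covariate. The electrode sentence is also in the past tense and may not describe current practice, although it is the only placement given.

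These points reduce the likely impact. They do not remove the conflict between the two sections or supply the missing rule.

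**Conclusion.** The point holds as a conflict in the procedure with a modest consequence. Followed as written, the plan records SC from the handling hand in 2 of 4 familiar-cue epochs per session, and in 12 of 28 cue-period epochs over the study, with no stated artefact rule. The expected result is extra noise in familiar-cue SC, not a shift between arms, provided handling is similar across arms. A null on familiar-cue SC would then be harder to read as absence of an effect.

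The size is unknown: the documents give no artefact variance, and the k values above are assumptions. Craving, blood pressure, the hypothesis 1 measures as listed, and the sample size are not affected by the electrode placement. The change is worth making because it is specific and cheap, not because the main conclusions depend on it.

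**What to change.** 1. Reconcile 3.D and 3.F so that cues are handled with the hand that carries no electrodes, by changing either the handling hand or the electrode site. Keep one arrangement across all sessions of a given participant; those already started finish as they began.
2. For sessions already run with the same hand, write a treatment-blind artefact-screening rule for the in vivo SC epochs into the data-reduction step in 3.H, and fix it before unblinding. Section 3.B says recruitment was near its end when enrolment was raised to 200, so this step may matter more than the first. State at the same time whether video and in vivo epochs are pooled, and how the peak is defined.
3. Pre-specify a sensitivity analysis with SC mean and peak from the video epochs only, for all participants and for the first-session covariate. It should not replace the main summary: it discards all in vivo SC and, under the illustration above, is noisier whenever k is below 2.
4. If different hands were used in practice, correct the text; nothing more is needed.

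The cost is one line of procedure, one data-reduction rule and one extra analysis. The downside is some added data-reduction work and, if the change is made mid-study, two hand arrangements in the data set. Record which arrangement each participant had.

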Study Design & Procedures. Non-treatment seeking cocaine-dependent (CD) individuals were recruited and randomized to receive either 40 mg propranolol (n=26) or a placebo (n=24) immediately following a “retrieval” session of CCE conducted in a controlled laboratory setting. In the retrieval CCE session, participants first viewed a 5 min ‘video’ depicting cocaine use and then handled ‘in vivo’ cocaine-related paraphernalia (e.g., simulated cocaine, \$20 bill, mirror, lighter, etc.) for an additional 5 min. After a 10 min break, this video-in vivo cue sequence was presented a second time. Measures of craving, heart rate (HR), and blood pressure (systolic, SBP; diastolic, DBP) and skin conductance (SC) were obtained at baseline (30 min prior to the first CCE), immediately after each video-in vivo cue sequence, and 15, 30 & 60 min after the second cue sequence. One day after the retrieval CCE session, a “test” CCE session was conducted that was identical to the retrieval session except no medication was administered. This test session served to assess the acute effects of the medication on craving and cue reactivity elicited by same cues presented in the retrieval session. To prevent drug use between the retrieval and test sessions, participants remained overnight in the Medical University of South Carolina’s Clinical and Translational Research Center (MUSC, CTCR). A third “follow-up” cue exposure session (identical to the test CCE session) was conducted one-week later.

Study Results. Initial analyses compared the groups on important demographic (e.g., age, gender, race, education, etc.) and clinical variables (e.g., age at first cocaine use, dollar amount of cocaine use over 90 days preceding study participation, number of days using over 90 days preceding study participation, route of administration). The analyses failed to identify any group differences (all p’s >.27). Finally, no group differences in baseline cocaine cue reactivity were detected on any primary outcome measure (all p’s > .17; baseline measures were the measures obtained during retrieval CCE session before medication).

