As in the R21, urn randomization will be used in assigning participants to the two propranolol groups (40PP & 80PP) and the placebo group (PBO)⁶⁸ while balancing treatment assignment on two variables. To maximize the power for a comparison of effect across gender and minimize confounding, gender will be balanced during the randomization. Dollar amount of cocaine use at baseline (pre-study involvement) is a likely prognostic factor on craving and other outcome measure and will be controlled during randomization. Specifically, the total dollar amount of cocaine use in the 3 months prior to study involvement will be determined (using the Timeline Follow-Back) and the following binary urn variable will be used: Participants with \leq \$1000.00 cocaine use pre-study involvement vs. participants with $>$ \$1000.00 cocaine use pre-study involvement. The effects of additional factors such as age and duration of use will be statistically controlled during the analysis (if necessary, see Data Analysis Plan below) since further stratification of the randomization could yield some stratum with very small expected sample sizes. This could lead to significant imbalance in the overall study.

Medication Administration

Immediately following the completion of the cue exposures in each of the first two retrieval CCE sessions (described below), one of three medications will be administered in accordance with randomization; 40 mg of immediate-release propranolol, 80 mg of immediate-release propranolol or a matching placebo will be administered. Medications will be compounded, packaged and dispensed by the MUSC Investigational Drug Service (IDS), who will also oversee the randomization procedures for the study and record the treatment assignment. The IDS provides 24-hour, seven-days-a-week, on-call availability to randomize, enroll, dispense medications and unblind as necessary.

D. Phase 1 Laboratory Session Procedures

Verification of Abstinence

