be used to determine plasma concentrations of the propranolol so that the association between propranolol level and treatment effects can be assessed; the timing of the blood draw was based on the observation that peak concentrations of propranolol are reached 90-min post administration.^{52,53} Also at this time, participants will be asked to complete a dual-item form that asks whether or not they thought they received propranolol or placebo and, for those who

Figure 4

thought they received propranolol, at what dose level (this data will be used to assess the effectiveness of the blind). Research staff will then escort the participant to a research dedicated hospital room where they will remain overnight. The second retrieval cue exposure session, occurring the following day at the same time, will be identical to the first in all respects, including the overnight stay at the Institute of Psychiatry (IOP). Prior to discharge from the IOP the next day, research staff will schedule a test/follow-up CCE session, remind the participant that it is important to maintain abstinence during the interim period between their inpatient stay and the test/follow-up session and also remind them that a significant portion of the compensation (i.e., \$75.00) available at the end of the test session will be contingent on a negative UDS. Our group has previously used a

modified version of the ‘fishbowl’ contingency management (CM)⁷¹ procedure to successfully achieve an 80% rate of UDS verified cocaine abstinence over a 3-day period. Since the ‘fishbowl’ CM procedure only offered a small probability of earning the level of monetary compensation we plan to guarantee in the proposed study, we expect the abstinence rates during the 2-4 day interim period to exceed 90%.

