1. Propranolol Dosing: We considered three dosage increases for use in the proposed study; 60 mg, 80 mg and 120 mg. The decision to employ 80 mg dosage was based on the following rationale. An 80 mg dosage represents a doubling of the 40 mg used in the R21, which is conceptually congruent with the doubling of the medicated retrievals from one in the R21. From a pharmacokinetic perspective, it is known that the bioavailability of propranolol is rather modest (Approximately 25%) and variable⁵⁷ so it was important that the dosage increase be sufficiently large to ensure an appreciable increase in plasma concentration and therefore, increased availability in the brain. Accordingly, it seemed likely that the 80 mg dosage would, on balance, achieve a substantial increase in central availability without sizably increasing risk of sinus bradycardia or a hypotensive episode. Furthermore, there have been several human laboratory^{89,90} and clinical studies⁹¹ on single or dual administrations of 80 mg or more of propranolol with no reported adverse effects. These observations, together with the fact that participants will remain at the CTTC for both medication administrations, increased our confidence about the safety of using 80 mg while at the same time achieving a biologically significant increase in propranolol plasma concentrations.

2. Number of Medicated retrieval sessions. While it is reasonable to assume that multiple medicated retrieval CCE sessions may cumulatively interfere with memory reconsolidation, there are no human laboratory or clinical studies to guide decision-making regarding incremental utility of additional medicated retrievals. As noted above, there are two infrahuman studies^{42,59} showing that 10 or more medicated retrievals achieve large DoR effects. However, these studies don't address the possibility that substantially fewer medicated retrievals may be all that is needed to achieve a significant augmentation of DoR. Moreover, high numbers of medicated retrieval sessions detract from the practical value and feasibility of DoR-based treatment. In the absence of any definitive empirical support regarding this decision, we have elected to double the number medicated retrievals employed in the R21. This decision represents an attempt to balance the goal of DoR augmentation with the increase in participant burden (i.e., more over night stays at CTTC), design complexity and difficulty interpreting the findings

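### The last scheduled heart rate and blood pressure reading is about 30 min after each dose, 60 min before the peak concentration the protocol cites, so no readings by arm are planned at that peak

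*Combined protocol and SAP*

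**What the plan says.** All places are in the combined protocol and SAP.

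- **Dosing.** Section 3.C, Medication Administration, places the dose as follows: "Immediately following the completion of the cue exposures in each of the first two retrieval CCE sessions". The Procedure paragraph of section 3.D agrees: "At the end of the CCE in the retrieval session, participants will receive their medication and complete all outcome measures".
- **Post-dose readings.** The same Procedure paragraph states: "all dependent measures will be obtained immediately after CCE sequence and at 15 min. and 30 min. time points following termination of CCE". Section 3.F, Physiological Measures, gives the same end point for HR and skin conductance ("they also are collected at baseline and at 15-min and 30-min follow-up time points; see figure 4") and ties BP to the times of the craving and mood scale.
- **Removal of equipment.** Section 3.D: "At the end of each retrieval session, research staff assisted the participant in removing the HR/SC leads and BP cuff".
- **Blood draw.** The participant stays another 60 min and is then bled; "the timing of the blood draw was based on the observation that peak concentrations of propranolol are reached 90-min post administration". A form asking which treatment the participant believes was given is completed at the same time, and staff then escort the participant to a hospital room for the night.
- **Risk weighed.** Section 3.I, item 1, expects 80 mg to raise central availability "without sizably increasing risk of sinus bradycardia or a hypotensive episode".
- **Preceding study.** Section 1.C reports that the R21, with one 40 mg dose, took its measures at baseline, after each cue sequence, "and 15, 30 & 60 min after the second cue sequence".
- **Safety text.** Section 3.L provides for physicians to monitor medical stability, for close follow-up of participants by clinical or research staff, and for dosing in a staffed unit with emergency medication and equipment. It names no HR or BP parameter and no time.

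**The concern.** The protocol treats 90 min as the pharmacologically informative time and brings the participant back for blood then. It also names two haemodynamic risks in its reasoning about the higher dose. Yet the written HR/BP schedule ends at 30 min, and the 90-min contact includes neither measure. This window is shorter than the R21's, although this trial adds a higher dose and a second administration; no reason is given.

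What is at stake is safety data. If the plan is followed as written, the trial will hold no HR or BP by arm (placebo, 40 mg, 80 mg) at the exposure peak it cites. It will then be unable to describe how 80 mg compares with 40 mg on the two risks it names at that time. The plasma concentration will also have no HR/BP reading taken alongside it.

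**Working it through.** No power or alpha figure bears on this point. The check is a timeline built from the protocol's own times.

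**1. Reproduce the blood-draw time.** Take the dose as time 0, equal to the end of cue exposure (sections 3.C and 3.D).
- Last scheduled HR/BP: 30 min.
- Further stay: 60 min.
- Draw: 30 + 60 = 90 min, which matches the peak time cited in sections 3.D and 1.C.

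**2. Gap from last reading to cited peak.** 90 − 30 = 60 min. The last reading is at 30/90, one third of the cited time to peak. If the dose lags the end of cue exposure by 0 to 5 min (my assumption), the last reading is 25 to 30 min and the draw 85 to 90 min after dose. The interval between reading and draw stays at 60 min.

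**3. Approximate clock (section 3.D).**

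| Event | Time |
|---|---|
| Baseline measures | 10:00 |
| First cue sequence (5 min video + 5 min in vivo) | 10:30 to 10:40 |
| Pause of 5 to 10 min | to 10:45–10:50 |
| Second cue sequence ends; dose | 10:55–11:00 |
| Last HR/BP (+30 min) | 11:25–11:30 |
| Blood draw (+60 min) | 12:25–12:30 |

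**4. Next scheduled reading.**
- After dose 1: the next day's baseline at about 10:00. From 11:30 that is 22.5 h after the last reading, and from an 11:00 dose it is 23 h.
- After dose 2: the test session, 2 to 4 days after discharge. Discharge is the day after dose 2, so this is about 3 to 5 days after dose.

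**5. Does other text supply the missing reading?**
- Figure 4 is not available to this review, but sections 3.D and 3.F both restate its time points in words. The 30-min end point does not depend on the figure.
- Section 3.L and the overnight stay describe supervision, with no HR or BP time.
- The adverse events form (section 3.F) is given at the end of the inpatient stay and at later visits, not at the 90-min draw.
- The overnight location itself is stated in two ways: section 3.A and the compensation text in 3.G say the CTRC, while section 3.D says the Institute of Psychiatry. It is therefore unclear which unit's routine vital signs, if any, would apply.

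**6. Comparison with the R21.** Taking its dose as given directly after the second cue sequence, the R21's last reading was at about 60 min, which is 90 − 60 = 30 min before the cited peak. The present schedule doubles that gap, from 30 to 60 min.

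**The case against.** The strongest reply is that the 15- and 30-min readings are research outcomes taken with laboratory equipment. Removing that equipment says nothing about clinical vital signs on a staffed unit. Section 3.L provides for medical monitoring, and participants stay overnight. Screening includes an electrocardiogram and excludes significant cardiovascular disease. The document is a grant research strategy that refers to a separate IND application, so unit orders need not appear in it. This stands in part. A reader might infer that bradycardia or hypotension would go undetected, but the documents support only the narrower statement that no HR or BP reading is scheduled in them after 30 min.

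A reader might also infer that the readings stop just before the risk is greatest. The documents give the time of peak plasma concentration, not of greatest haemodynamic effect, and do not equate the two. Nor is exposure negligible at 30 min. Assume a one-compartment model, C(t) ∝ exp(−ke·t) − exp(−ka·t), with ke = ln 2 / half-life, ka set so that the peak is at 1.5 h, and the protocol's half-life of 3 to 4 h. The ratio C(0.5 h)/C(1.5 h) is then 0.409/0.595 = 0.69 for 3 h (ke 0.231, ka 1.46) and 0.488/0.692 = 0.71 for 4 h (ke 0.173, ka 1.69). On that assumption the last reading is taken at about 70% of peak concentration.

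It can further be said that no planned analysis suffers. That stands. Peak-time HR/BP is not an outcome. Section 3.F says that physiological responses in the second medicated session bear on no hypothesis. The plasma level is to be regressed on outcomes at the test/follow-up sessions. The 80 mg dose is also supported by prior human studies and the inpatient setting, not by data this trial must produce.

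What the reply does not remove is the mismatch. The plan states an explicit schedule, that schedule ends before the protocol's own peak, and none of the safeguards supplies a reading there.

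**Conclusion.** The point holds as a gap in planned safety data. The last HR/BP reading scheduled in the documents is about 30 min after each dose, 60 min before the cited 90-min peak, and this happens after both doses in all arms. No HR/BP data by arm are planned at that peak, although bradycardia and hypotension were weighed in choosing 80 mg and the R21 measured 30 min longer.

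This rests on dosing at, or within a few minutes of, the end of cue exposure, and on the written time points in sections 3.D and 3.F being complete. It does not rest on a pharmacokinetic model. It does not establish that participants are unmonitored, that risk peaks with concentration, or that any hypothesis test is compromised. The change is worth making because it is cheap and adds safety data on the dose comparison.

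**What to change.** Reconcile the measurement schedule in sections 3.D (Procedure) and 3.F (Physiological Measures) with the cited 90-min peak and with the safety text in sections 3.I (item 1) and 3.L. There are two ways to do this:

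- keep the cuff and HR leads on, or re-apply them, and record HR and BP during the existing wait at 60 min (as in the R21) and at the existing 90-min blood draw, after both doses; or
- if the unit already takes vital signs around those times, state that schedule and which unit it belongs to, and capture the readings in the study database.

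In either case, add to the Data Analysis Plan a descriptive summary of these readings by arm and dose occasion. Any review step or action threshold is for the investigators.

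The cost is two extra readings per dose, four per participant over the two doses, taken by staff already present during a wait and a draw already scheduled. The participant wears the cuff and leads for about an hour longer or has them re-applied. No visit, hypothesis or sample size changes.
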